7.2. Study Population and Setting

7.2.1. Inclusion Criteria

People without HIV in OPERA (Obj 1)

- i. ≥ 1 clinical encounter in OPERA during the calendar year of interest
- ii. ≥ 18 years old at the first clinical encounter during the calendar year of interest
- iii. No evidence of prior HIV diagnosis

People with a new HIV diagnosis (Obj 1.a)

- i. Incident HIV diagnosis (new HIV diagnosis/positive HIV test/detectable HIV RNA viral load) identified in Obj 1

PrEP users (Obj 2-5)

- i. HIV-negative
- ii. ≥ 18 years of age
- iii. Started any new PrEP formulation
 - Analysis #1: between 21DEC2021 and 30JUN2023
 - Analysis #2: between 21DEC2021 and 30JUN2024
- iv. With or without prior PrEP use (a different formulation or a gap ≥ 61 days without any PrEP immediately prior to the index PrEP; the same formulation may have been used ≥ 61 days before starting the index PrEP)

People who could benefit from PrEP (Obj 6)

- i. HIV-negative
- ii. ≥ 18 years of age

- iii. ≥ 1 clinical encounter in OPERA during the inclusion period
 - Analysis #1: between 21DEC2021 and 30JUN2023
 - Analysis #2: between 21DEC2021 and 30JUN2024
- iv. Any of the following indications for PrEP¹¹:
 - Bacterial STI in past 12 monthsⁱ (gonorrhea, syphilis, chlamydia)⁷
 - Alcohol use disorder⁷
 - Illicit non-injection drug use⁷
 - Injection drug use^{7, 14}
 - Black women¹⁴
 - Transgender women¹⁴
 - Men who have sex with men¹⁴
 - All individuals aged 18-24 yearsⁱⁱ¹⁴
 - Any history of PrEP use

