7.3.2. Outcome definitions

People without HIV in OPERA (Obj 1)

Incident HIV diagnosis

- New HIV diagnosis and/or detectable HIV RNA and/or positive antigen/antibody test
- All potential incident HIV diagnoses will be subject to a thorough chart review for confirmation

People with a new HIV diagnosis (Obj 1.a)

Not applicable

Protocol for Non-Interventional Studies PASS Studies and Non-PASS Studies (4.0) March 2024

Template Doc ID: TMF-15706807

Parent Doc ID: VQD-SOP-066694

PrEP users (Obj 2-5)

Incident HIV diagnosis

- Frequency of new HIV diagnosis and/or detectable HIV RNA and/or positive antigen/antibody test
- Months from start of PrEP type (oral vs. LA) to HIV diagnosis
- Rate of incident HIV diagnoses per 100 person-years of follow-up
 - Within the first 12 months after index PrEP start
 - Through study end (Analysis #1: 30JUN2024; Analysis #2: 30JUN2025)
 - Follow-up (FU) will be censored at first of:
 - HIV diagnosis
 - Death
 - Study end (Analysis #1: 30JUN2024; Analysis #2: 30JUN2025)
 - Loss to follow-up (12 months after last clinical contact)
 - 12 months after index date
- All potential HIV acquisitions will be subject to a thorough chart review for confirmation
 - All lab results, diagnoses, ART prescriptions and clinician notes available in OPERA on or after the potential HIV acquisition was identified will be reviewed

PrEP coverage

- Oral PrEP coverage:
 - Proportion of days of access to oral PrEP in the 12-months following index PrEP initiation
 - Follow-up (FU) will be censored at first of:
 - a) Death
 - b) Study end (Analysis #1: 30JUN2024; Analysis #2: 30JUN2025)
 - c) Loss to follow-up (12 months after last clinical contact)
 - d) 12 months after index date
 - Access to oral PrEP will be determined based on the dates and days of supply for each prescription (e.g., a prescription for 30 pills/month with 3 refills provides 90 days of access)
 - a) Each calendar day will only be counted once, even if there is an overlap between access from the prior prescription and start of the next prescription.

$$\% \text{ access} = \frac{\sum \text{Number of pills in each prescription}}{\text{Number of FU days}} \times 100\%$$

- LA PrEP coverage:
 - Proportion of days of coverage by CAB LA over follow-up
 - Follow-up (FU) will be censored at first of:
 - a) Death
 - b) Study end (Analysis #1: 30JUN2024; Analysis #2: 30JUN2025)

- c) Loss to follow-up (12 months after last clinical contact)
- d) 12 months after index date

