ANNEX 1 TABLES

Table shells for Analysis #1 are presented. Tables will be identical for Analysis #2, with the exception that study periods will be updated.

Table 1. Identification of the population of people without HIV in OPERA (Analysis #1)

	Included N (%)	Excluded N (%)
All individuals in OPERA		
≥1 clinical encounter between 01JAN2021 and 31DEC2021		
≥18 years old at first clinical encounter in 2021		
No evidence of HIV diagnosis before the first clinical encounter in 2021 [2021 pop]		
≥1 clinical encounter between 01JAN2022 and 31DEC2022		
≥18 years old at first clinical encounter in 2022		
No evidence of HIV diagnosis before the first clinical encounter in 2022 [2022 pop]		
≥1 clinical encounter between 01JAN2023 and 31DEC2023		
≥18 years old at first clinical encounter in 2023		
No evidence of HIV diagnosis before the first clinical encounter in 2023 [2023 pop]		

Table 2. Annual HIV incidence among people without HIV (Analysis #1)

	People without HIV, N	Incident HIV, ^a n (%)
2021		
2022		
2023		

^a New HIV diagnosis or positive HIV test (RNA, antigen/antibody)

Table 3. PrEP use among people with incident HIV (Analysis #1)

	People with incident HIV ^a N =
Never received PrEP, n (%)	
Ever received PrEP, n (%)	
Total number of days on PrEP, median (IQR) ^b	
Number of PrEP formulations received	
1, n (%)	
2, n (%)	
3, n (%)	
Any gaps between formulations, n (%) ^c	
Duration of gaps between formulations, median (IQR)	
PrEP use within ≤12 months before/on HIV diagnosis, n (%)	
Oral PrEP, n (%)	
TDF/FTC, n (%)	
TAF/FTC, n (%)	
CAB LA, n (%)	
Past PrEP use >12 months before HIV diagnosis, n (%)	
Oral PrEP, n (%)	
TDF/FTC, n (%)	
TAF/FTC, n (%)	
CAB LA, n (%)	

^a New HIV diagnosis or positive HIV test (RNA, antigen/antibody)

^b Including all formulations; gaps without PrEP do not count toward the total number of days on PrEP

^c Gap ≥31 days after oral PrEP, gap ≥37 days after first CAB LA injection, or gap ≥67 days after 2nd or subsequent CAB LA injection

Table 4. Identification of the PrEP users population

	Included N (%)	Excluded N (%)
All individuals in OPERA		
Ever received a PrEP prescription/injection in OPERA while HIV negative		
Start a new PrEP formulation (TDF/FTC, TAF/FTC, CAB LA) ^a between 21DEC2021 and 30JUN2023		
≥18 years old at start of index PrEP regimen		

^a Switch from one formulation to another or return to the same formulation after a pause ≥61 days without PrEP

Table 5. PrEP formulations used among PrEP users

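### Objective 1 can count HIV first recorded at a person's first-ever OPERA encounter as incident, and Objective 1a then defaults such cases to never having received PrEP

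*Protocol*

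**What the plan says.** Section 7.2.1 of the protocol admits a person to the Objective 1 population for a calendar year on three conditions: at least "1 clinical encounter in OPERA during the calendar year of interest", age 18 or over, and "No evidence of prior HIV diagnosis". Annex Table 1 turns the third condition into a cut-off at that year's first encounter: "No evidence of HIV diagnosis before the first clinical encounter in 2021 [2021 pop" for 2021, with the same rule for 2022 and 2023.

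The outcome in Section 7.3.2 is "New HIV diagnosis and/or detectable HIV RNA and/or positive antigen/antibody test". The footnote to Annex Tables 2 and 3 puts it as "New HIV diagnosis or positive HIV test (RNA, antigen/antibody". Section 7.3.2 adds one safeguard for Objective 1: "All potential incident HIV diagnoses will be subject to a thorough chart review for confirmation".

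Annex Table 2 reports the resulting number and percentage per year under a title that calls it annual HIV incidence among people without HIV. Under Section 7.2.1, every Objective 1 case passes to Objective 1a. Annex Table 3 then divides the cases into "Never received PrEP, n" (%) and ever received PrEP. It has no requirement on observable history and no row for history that could not be seen.

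**The concern.** An incidence figure needs people who were at risk when observation began. Someone whose first OPERA encounter falls in the year usually has no earlier OPERA record on which to fail the HIV-free condition. If HIV is recorded at that same encounter, the person joins the population and the numerator together, with no time observed without HIV.

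Two results are affected. The yearly percentage combines new diagnoses in people already under observation with HIV found on entry to the database. The second part depends on how many new people the clinics take in, so a change across 2021 to 2024 could reflect recruitment. In Objective 1a, a person with no earlier OPERA record has no earlier OPERA prescriptions either. Absence of data is then reported as absence of PrEP, in the one table meant to describe PrEP history among people diagnosed with HIV.

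**Working it through.** The protocol states no expected incidence, sample size or precision for Objectives 1 and 1a, so there is no planned figure to reproduce. The check is to apply the rules to four kinds of patient.

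| Patient | Entry rule (7.2.1, Annex Table 1) | Outcome and chart review (7.3.2) | Annex Table 3 |
|---|---|---|---|
| A. Known HIV, transfers care, chart shows it | Fails if the chart evidences an earlier diagnosis | If flagged, labs, notes or ART should expose it | Mostly absent |
| B. Long-standing infection never diagnosed, found at first OPERA encounter | Passes | HIV correctly confirmed; counted | Never, unless outside PrEP is charted |
| C. Recent infection, first diagnosed at first OPERA encounter | Passes | HIV correctly confirmed; counted | Never, unless outside PrEP is charted |
| D. Seen earlier in OPERA without HIV evidence, later diagnosed | Passes | HIV correctly confirmed; counted | OPERA PrEP history observable since entry |

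B, C and D share one cell of Annex Table 2 and one column of Annex Table 3. Only D was observed before diagnosis. Confirming that HIV is present does not separate B from C or D.

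**Direction of the Objective 1a error.** Let T be the true never-PrEP share among all cases, s the share of cases of type B or C, and u the share of those who did use PrEP elsewhere without it being charted. Then

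reported never share = T + s × u.

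The error is never negative from this source. It is zero only if s or u is zero. It applies to genuinely new diagnoses (C) as much as to old infection (B), so it does not depend on a transfer rate.

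**Size.** The protocol gives neither s nor u. To show only how the formula behaves, assume T = 70% and u = 30%. Write s = fq/(i + fq), where f is the share of the year's population new to OPERA, q the share of those counted as cases at entry, and i the annual proportion diagnosed otherwise. All are assumptions.

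- f = 10%, q = 0.05%, i = 0.5%: fq = 0.005%, s = 0.005/0.505 = 1.0%, reported 70.3%.
- f = 30%, q = 0.2%, i = 0.2%: fq = 0.06%, s = 0.06/0.26 = 23.1%, reported 70 + 0.231 × 30 = 76.9%.
- f = 50%, q = 1%, i = 0.2%: fq = 0.5%, s = 0.5/0.7 = 71.4%, reported 70 + 0.714 × 30 = 91.4%.

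The spread from 70.3% to 91.4% reflects the inputs chosen. Nothing in the protocol selects among them.

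**Is the point handled elsewhere?** Annex Table 9 reports a negative HIV test at PrEP start for PrEP users, and Annex Tables 7 and 31 report months since first OPERA visit. The Objective 1 and 1a tables have neither. Section 7.9 covers test-dependent ascertainment, timing error and care received at other practices. It does not mention HIV already present at entry or PrEP history that predates the record. Section 7.4 gives average follow-up of 1.2 years, so the category for use more than 12 months before diagnosis will often rest on little observable time.

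**The case against.** The strongest reply has four parts.

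First, "No evidence of prior HIV diagnosis" is not limited to entries made earlier in OPERA. A transferring patient whose chart carries a past diagnosis date or a history of HIV care has such evidence and can be excluded. This stands. A reader might infer that every newcomer with known HIV passes the criterion, and the text does not support that.

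Second, chart review is a real safeguard. Its detailed scope, given under Objectives 2–5 and 6, is "All lab results, diagnoses, ART prescriptions and clinician notes available in OPERA on or after the potential HIV acquisition was identified will be reviewed". A reader might infer that this leaves the review blind to earlier history. For someone whose trigger is the first-ever encounter, nearly all OPERA records fall on or after it, so little is lost. That scope is also not stated for Objective 1, and a detailed adjudication rule may properly sit in the analysis specifications. This stands for type A. It does not help with type B, where HIV is correctly confirmed and the person is still counted.

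Third, the objective concerns HIV diagnoses, not infections, so a first diagnosis at a first visit is a genuine new diagnosis. This stands, and it is why such cases should not be removed from the overall count. It does not make them incident cases in a population observed without HIV, as the title of Annex Table 2 suggests.

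Fourth, an earlier encounter without a test does not prove the person was HIV-negative. This also stands, and a documented negative test is the better criterion.

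**Conclusion.** The point holds in a limited form. Objective 1 requires no earlier HIV-free encounter or negative test, so its yearly percentage can include people never observed without HIV, and chart review that does its job correctly will not set them apart. The Objective 1a consequence is firmer: unobservable PrEP history is reported as never, and the error runs in one direction. That conclusion assumes only that some cases are first recorded at entry and that some of these people used PrEP elsewhere without it being charted.

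No size is claimed. A reader might try to build an inflation factor from the 85,396 active people with HIV and 294,314 without in Table 2 of Section 7.4. Those counts cover contact in the previous 24 months and all ages, whereas Objective 1 is yearly and restricted to adults. The transfer rate, the rate at which review misses transfers and the true incidence would all have to be assumed. A virally suppressed transfer with no repeat serology also need not trigger the outcome. Nor do the documents support saying that transferred patients make up a material part of the count.

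The study is descriptive and this does not invalidate it. It limits what the yearly percentage and the PrEP-history split can be taken to mean.

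**What to change.** **Annex Table 2.** Keep the overall count of new diagnoses. Add rows splitting it into (a) people with at least one earlier OPERA encounter without HIV evidence, preferably with a documented negative HIV test, and (b) people whose HIV was first recorded at their first-ever OPERA encounter. Apply the same prior-observation rule to the denominator of row (a). A person whose only OPERA encounter is the first-ever one should be in neither its numerator nor its denominator; otherwise non-cases who could never become cases would lower the percentage. Use row (a) for any statement about incidence or its trend.

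**Section 7.2.1 and Annex Table 1.** State the prior-observation rule that defines row (a).

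**Annex Table 3.** Report PrEP history separately for the two groups. Relabel the never row as *No PrEP recorded in OPERA*. For first-encounter cases, mark earlier PrEP history as not observable unless it is charted.

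**Cost.** One flag is needed, and it can be derived from time since first OPERA visit, which Section 7.3 already lists. Two or three rows are added. The incidence row has a smaller numerator and omits true new diagnoses made at a first visit, but these stay visible in row (b) and in the overall count.

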7.7.1. Primary analysis

7.7.1.1. Main Analytical approach

People without HIV in OPERA (Obj 1)

For each calendar year, the number and percentage of new HIV diagnoses will be reported out of all individuals receiving care at an OPERA clinic.

People with a new HIV diagnosis (Obj 1.a)

Among newly diagnosed people with HIV, PrEP use (never, use within ≤ 12 months before diagnosis, use > 12 months before diagnosis) and PrEP characteristics will be described using counts and proportions for categorical variables and median and interquartile ranges for continuous variables.

PrEP users (Obj 2-5)

(Obj 2) Baseline demographic and clinical characteristics will be described at the start of PrEP use during the study period, by regimen type (oral or LA), using median and interquartile ranges for continuous variables and counts and proportions for categorical variables.

Individuals contributing to both the oral and CAB LA PrEP groups may be included in both groups.

(Obj 3) The number, percentage, and incidence rate (per 100 person-years) of incident HIV diagnoses within 12 months of starting index PrEP and through study end will be described by route of administration (time-updated, oral or LA). The timing of HIV testing relative to PrEP start and HIV diagnosis will be described to assess to possibility of attributing HIV acquisition to the correct PrEP type. Incidence rates of HIV diagnoses (per 100 person-years) within 12 months of start and through study end will be estimated using time-updated univariate Poisson regression for each regimen type (time-updated, oral vs LA) to account for varying duration of follow-up.

(Obj 4) The percentage of days with access to oral PrEP and the percentage of days with coverage by CAB LA PrEP will be described over the first 12 months after index PrEP initiation.

(Obj 5) The frequency and rate (per 100 person-years) of HIV testing, STI screening, and STI diagnoses at index PrEP initiation and in the 12-months after index PrEP initiation.

Characteristics of the tests conducted will also be described. Frequency and type of tests

performed will be described by type of healthcare provider ordering the test and clinic type. Rates of HIV and STI tests over the first 12 months will be estimated using time-updated univariate Poisson regression for each regimen type (oral vs LA).

People who could benefit from PrEP (Obj 6)

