	PrEP users
PrEP formulation at index, N	
Oral, n (%)	
TDF/FTC, n (%)	
TAF/FTC, n (%)	
CAB LA, n (%)	
Switch from oral to CAB LA PrEP within 12 months of initiating index oral PrEP, n (%)	
Switch from CAB LA to oral PrEP within 12 months of initiating index CAB LA, n (%)	

Table 6. Demographic characteristics at start of PrEP regimen^a among PrEP users

	Oral PrEP N=	CAB LA PrEP N=
Age		
Median (IQR)		
18-29		
30-39		
40-49		
50-59		
≥60		
Sex		
Female		
Male		
Unknown		
Transgender, n (%) ^b		
Race		
Black		
Asian		
White		
Mixed or Other races		
Unknown race		
Hispanic ethnicity		
US Region		
Northeast		
South		
Midwest		
West		
US Territories		
Marital status		
Single		
Married/Domestic Partner		
Widowed		
Separated/divorced		
Unknown		
Payer ^c		
Medicaid		
Medicare		
Commercial Insurance		
Other		
Unknown		

^a Individuals who switched PrEP type during follow-up are included in both groups

^b Gender identity is not reported by all clinics and physicians; available data may be insufficient to infer cisgender identity.

^c Payer categories are not mutually exclusive.

Table 7. Clinical care characteristics at start of PrEP regimen^a among PrEP users

	Oral PrEP N=	CAB LA PrEP N=
Months since first OPERA visit, median (IQR)		
Any visits with OPERA provider within 12 months prior to start, n (%)		
Number of visits, median (IQR)		
Prescriber specialty, n (%)		
Infectious diseases		
General practice		
Other		
Unknown		
Clinic type, n (%)		
Healthcare center		
Wellness center		
Other		

^a Individuals who switched PrEP type during follow-up are included in both groups

Table 8. Sexual health characteristics at start of PrEP regimen^a among PrEP users

	Oral PrEP N=	CAB LA PrEP N=
History of STI (ever)		
Syphilis		
Gonorrhea		
Chlamydia		
Chancroid		
Lymphogranuloma venereum		
Mycoplasma genitalium		
Herpes Simplex-2		
Trichomoniasis		
Human papilloma virus/genital warts		
History of STI (past 3 months)		
Syphilis		
Gonorrhea		
Chlamydia		
Chancroid		
Lymphogranuloma venereum		
Mycoplasma genitalium		
Herpes Simplex-2		
Trichomoniasis		
Human papilloma virus/genital warts		

^a Individuals who switched PrEP type during follow-up are included in both groups

Table 9. Incident HIV^a within 12 months of index and through study end among PrEP users

	Oral PrEP N=	CAB LA PrEP N=
Within 12 months of index		
HIV diagnosis, n (%)		
Months from start of PrEP type to HIV diagnosis, median (IQR)		
Negative HIV test within 2 weeks before/on start of PrEP type, n (%)		

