Through study end		
HIV diagnosis, n (%)		
Months from start of PrEP type to HIV diagnosis, median (IQR)		
Negative HIV test within 2 weeks before/on start of PrEP type, n (%)		

^a Incident HIV is only counted for the PrEP type used at the time of diagnosis

Table 10 Incidence rate of HIV^a within 12 months of index and through study end among PrEP users

	Oral PrEP N=	CAB LA PrEP N=
Within 12 months of index		
HIV diagnosis, n (%)		
Person-years of follow-up		
IR per 100 py (95% CI)		
Through study end		
HIV diagnosis, n (%)		
Person-years of follow-up		
IR per 100 py (95% CI)		

^a Incident HIV is only counted for the PrEP type used at the time of diagnosis

Table 11. Oral PrEP coverage within 12 months of index among **oral** PrEP users

	Oral PrEP N=
Mean # pills prescribed (SD)	
Median # of pills prescribed (IQR)	
Mean days of follow-up on oral PrEP ^a (SD)	
Median days of follow-up on oral PrEP ^a (IQR)	
Mean % access (total pills prescribed/days of follow-up) (SD)	
Median % access (total pills prescribed/days of follow-up) (IQR)	

^a If index PrEP is oral: shortest of (a) days from index to first CAB LA injection or (b) 12 months after index; if index PrEP is CAB LA injections: shortest of (a) days from start of switch to oral PrEP to study end or (b) 12 months after index

Table 12. CAB LA PrEP coverage within 12 months of index among CAB LA PrEP users

	CAB LA PrEP N=
Mean days covered ^a (SD)	
Median days covered ^a (IQR)	
Mean days of follow-up on CAB LA PrEP ^b (SD)	
Median days of follow-up on CAB LA PrEP ^b (IQR)	
Mean % coverage (days covered/days of follow-up) (SD)	
Median % coverage (days covered/days of follow-up) (IQR)	

^b Total days between injections, up to 37 days between the first 2 injections or up to 67 days between subsequent injections

^a If index PrEP is oral: shortest of (a) days from index to first CAB LA injection or (b) 12 months after index; if index PrEP is CAB LA injections: shortest of (a) days from first CAB LA injection to study end or (b) 12 months after index

Table 13. Incidence rate of HIV testing events within 12 months of index among PrEP users^a

	Oral PrEP N=	CAB LA PrEP N=
Total # HIV testing events within 12 months of index, n		
Person-years of follow-up		
IR per 100 py (95% CI)		

^a HIV testing events are only counted for the PrEP type used at the time of diagnosis

Table 14. Frequency and type of HIV testing among PrEP users^a

	Oral PrEP N=	CAB LA PrEP N=

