HIV test within 14 days before/on day of PrEP type start, n (%)		
Test type		
RNA only, n (%)		
Quantitative RNA test, n (%)		
Qualitative RNA test, n (%)		
Ag/Ab only, n (%)		
Rapid test only, n (%)		
Both RNA and Ag/Ab, n (%)		
Quantitative RNA test, n (%)		
Qualitative RNA test, n (%)		
Both RNA and rapid test, n (%)		
RNA, Ab/Ag and rapid tests, n (%)		
Days from test to PrEP type start, median (IQR)		
Any HIV test within 12 months after PrEP type start, n (%)		
Total number of testing events ^b , N		
Test type		
RNA only, n (%)		
Quantitative RNA test, n (%)		
Qualitative RNA test, n (%)		
Ag/Ab only, n (%)		
Both RNA and Ag/Ab, n (%)		
Quantitative RNA test, n (%)		
Qualitative RNA test, n (%)		
Number of HIV testing events ^b per person, median (IQR)		
Average testing interval per person (#testing events /weeks on PrEP type), median (IQR)		
Testing on schedule (oral: every 3 months (76-104 days); CAB LA: ±14 days of each injection), n (%)		

^a Tests are only counted for the PrEP type used at the time of diagnosis

^b Multiple HIV tests on the same day count as one testing event

Table 15. Frequency and type of HIV tests among oral PrEP users, by healthcare provider type ^a

	MD or DO	Physician Assistant	Nurse Practitioner	Other/unknown
Total number of HIV testing events ^b ordered				
Test type				
RNA only, n (%)				
Quantitative RNA test, n (%)				
Qualitative RNA test, n (%)				
Ag/Ab only, n (%)				
Rapid test only, n (%)				
Both RNA and Ag/Ab, n (%)				
Quantitative RNA test, n (%)				
Qualitative RNA test, n (%)				
Both RNA and rapid test, n (%)				
RNA, Ab/Ag and rapid tests, n (%)				
Testing on schedule (≤14 days before/at start or 3 months (76-104 days) after the last test, as applicable), n (%)				

^a Assessed at the test-level

^b Multiple HIV tests on the same day count as one testing event

Table 16. Frequency and type of HIV tests among CAB LA PrEP users, by healthcare provider type^a

	MD or DO	Physician Associate	Nurse Practitioner	Other/unknown
Total number of HIV testing events ^b ordered				
Test type				
RNA only, n (%)				
Quantitative RNA test, n (%)				
Qualitative RNA test, n (%)				
Ag/Ab only, n (%)				
Rapid test only, n (%)				
Both RNA and Ag/Ab, n (%)				
Quantitative RNA test, n (%)				
Qualitative RNA test, n (%)				
Both RNA and rapid test, n (%)				
RNA, Ab/Ag and rapid tests, n (%)				
Testing on schedule (≤14 days before/at first injection or ±14 days of each subsequent injection, as applicable), n (%)				

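### The counting rule in Annex 1 Tables 9 and 10 can record HIV already present when a PrEP type starts as incident HIV on that type

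*Protocol*

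**What the plan says.** **Attribution.** Footnote a to Annex 1 Tables 9 and 10 reads: "Incident HIV is only counted for the PrEP type used at the time of diagnosis". Exposure is time-updated by type, oral or LA (7.3.1).

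**Case definition.** For PrEP users, 7.3.2 gives "Frequency of new HIV diagnosis and/or detectable HIV RNA and/or positive antigen/antibody test". It has no exclusion for evidence dated on the day a type starts.

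**Entry.** Section 7.2.1 lists "i. HIV-negative" without naming a test, a window or a rule for a sample still pending. The matching row of Annex 1 Table 4 is "Ever received a PrEP prescription/injection in OPERA while HIV negative". The index date is the start of the first PrEP regimen in the study period (7.1, Table 1).

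**Testing at start.** Annex 1 Table 14 tabulates "HIV test within 14 days before/on day of PrEP type start, n" and Table 9 tabulates "Negative HIV test within 2 weeks before/on start of PrEP type, n". Both are counts with percentages, not conditions. Table 10, which holds the rate, has no such row.

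**Acknowledgement.** For Objective 3, 7.7.1.1 says the timing of HIV tests will be described, to judge whether the plan is "attributing HIV acquisition to the correct PrEP type". Potential cases get a confirmatory chart review of records from the time the signal was identified onward (7.3.2).

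**Past PrEP use.** Section 7.3.1 classifies PrEP use by the time before diagnosis. The corresponding row of Annex 1 Table 3 reads "before/on HIV diagnosis, n".

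**The concern.** An infection that predates a PrEP type is not an event on that type. The at-risk period should begin in people shown, as far as testing allows, to be free of HIV when the type starts. Here the event rule runs from the day of start with no such condition. The Protocol itself expects samples on that day: the Rationale (section 5) places CAB LA testing at the injection, and 7.3.2 accepts a test at the first injection as on schedule.

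What is at stake is the Table 10 rate, which answers Objective 3. For CAB LA that rate will rest on few events, so one wrongly attributed case is visible. Moving from oral PrEP is a common way into the CAB LA group, so infections acquired on oral PrEP have a real route into the CAB LA numerator.

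**Working it through.** **1. Following two people through the rules**

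- *Switch during the study.* A participant enters on oral PrEP and meets the HIV-negative criterion at index. Months later the first CAB LA injection is given and a sample is drawn that day. The sample is positive. Nothing reapplies the entry criterion at the change of type. The type in use at diagnosis is CAB LA, so the footnote books a CAB LA event with about zero months of exposure.
- *No test at start.* A participant starts a type without a test. Tables 9 and 14 show that such people are in the cohort. HIV is found at a later test and counted for the type then in use. Chart review can confirm the HIV, but it cannot create a negative result at start.

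**2. Group sizes (7.5)**

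- Index starters: 12,110 + 9,740 + 384 = 22,234. This reproduces the stated total.
- Oral starters: 12,110 + 9,740 = 21,850.
- CAB LA: 384 + 292 = 676, but the Protocol states 767. The difference is 91; reaching 767 would need 767 − 384 = 383 switchers. Both totals are carried below.
- Switchers as a share of CAB LA users: 292/676 = 43%, or 383/767 = 50%.

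**3. Weight of one misattributed case, 12-month rate**

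Added rate = 100 / person-years, at a maximum of one person-year per person.

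| Group | Person-years | Added per 100 person-years |
|---|---|---|
| CAB LA, 767 | 767 | 100/767 = 0.130 |
| CAB LA, 676 | 676 | 100/676 = 0.148 |
| Oral | 21,850 | 100/21,850 = 0.0046 |

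One case weighs about 28 to 32 times more for CAB LA. For context, with 676 person-years zero events give a rate of 0 (exact 95% CI 0 to 0.55), and one event gives 0.15 (0.004 to 0.82).

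**4. Weight per case is not expected bias**

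Let π be the prevalence of HIV at the start of a type and T the mean person-years on it. The expected added rate is 100π/T, and group size cancels. The Protocol gives neither quantity, so the values here are assumptions.

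- π = 0.2%, T = 1: expected cases are 0.002 × 676 = 1.4 (or 0.002 × 767 = 1.5) for CAB LA and 0.002 × 21,850 = 43.7 for oral. The added rate is 0.20 per 100 person-years in both.
- Over π = 0.1% to 0.5% with T = 1, the added rate is 0.10 to 0.50, again equal in both.
- If switchers average half a year on CAB LA inside the 12-month window: 384 + 0.5 × 292 = 530 person-years. At π = 0.2% CAB LA gains 100 × 1.352/530 = 0.26, and oral gains 100 × 43.7/(21,850 − 146) = 0.20.
- That ordering reverses if prevalence at oral start exceeds prevalence at CAB LA start by a factor of (676/530)/(21,850/21,704) = 1.27. With 383 switchers the factor is 1.32.

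**The case against.** The strongest reply has four parts.

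- *A positive index-day sample fails the entry criterion.* This is a fair reading, and the Rationale says testing before initiation serves to confirm absence of HIV. A reader might infer that every positive sample on an index day is counted as incident; the text does not say so. It leaves open whether status goes by sample date or result date. The objection does not reach later switches, because the criterion is stated for entry only.
- *The problem is seen and displayed.* True: 7.7.1.1 describes test timing, and Table 9 reports months from start of type and the negative-at-start count beside the cases. The limitations section also concedes error in diagnosis timing. But this is description. No case is removed or reassigned, and no restricted rate is produced.
- *The details belong in the analysis specifications.* How HIV-negative is put into operation may well sit there. The attribution rule and the Table 10 shell, however, are already fixed in the Protocol.
- *The study is descriptive, with no test between types.* This limits the harm but does not make the reported rate correct.

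One caution about the remedy also stands. Section 7.2.1 admits people after at least 61 days without PrEP, so charging HIV at start to the preceding type as a blanket rule could burden that type with infections acquired off PrEP.

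**Conclusion.** The point holds as a flaw in a stated rule. HIV present at the start of a type can enter Table 10 as incident on that type, most clearly for oral-to-CAB LA switchers whose first-injection sample is positive, and also for people untested at start. The planned descriptions reveal such cases but leave the rate as it is.

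One case moves the 12-month CAB LA rate by 0.13 to 0.15 per 100 person-years and the oral rate by about 0.005, assuming one full person-year each. Shorter time on a type raises these figures. Each case adds less to the rate through study end, which has more person-time.

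A reader might infer that the CAB LA rate is the more inflated of the two. The documents do not support that. The larger weight per case reflects group size alone; at equal prevalence and equal time on type the expected inflation is the same, and the direction turns on quantities the Protocol does not give. Nor can a percentage inflation be stated, because no expected HIV rate is given.

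The change should be made: it corrects a fixed rule at little cost.

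**What to change.** 1. In Tables 9 and 10, do not count as incident on a PrEP type any HIV evidenced by a sample drawn on or before the start date of that type. List these cases on a separate line as HIV present at start.
2. Attribute such a case to the preceding type only if that type was still in use with no gap. State which gap length applies: 7.2.1 uses at least 61 days, while Annex 1 Table 3 uses at least 31 days after oral PrEP.
3. Add a Table 10 row with events, person-years and rate among people with a documented negative antigen/antibody or RNA test within 14 days before or on the start of the type. This is the only step that addresses people untested at start. It removes the detectable part of the problem, not infections too recent to detect.
4. Minor: reconcile the Annex 1 Table 3 row with 7.3.1, so that PrEP first started on the diagnosis date is not counted as prior use.
5. Reconcile 384 + 292 with 767, since the CAB LA denominator depends on it.

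The cost is two rule sentences and one table row, from data the plan already extracts. The downside is slightly fewer counted events and a smaller denominator in the restricted row.
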